**Data Safety and Monitoring:**

Patient Safety: Adverse Events (AE) and Serious Adverse Events (SAE):

Any untoward medical occurrence in a patient temporarily associated with the use of Lialda whether or not considered related will be recorded. SAE is defined as life threatening event or death. Safety data will be assessed by the age and race. The study side effects will be reviewed by the PI, and unexpected side effects will be reported to the IRB. All adverse events will be recorded and reported to Shire Developmental Inc.

The Data Safety Monitoring Plan consists of setting up a Data Safety Monitoring Board (DSMB). The DSMB will consist of a physician ([name], M.D., Division of Infectious Disease), a pharmacist ([name]) and a biostatistician ([name]). The board will meet every 4 months to review the study's progress and endpoints, monitoring of safety data (adverse events or serious adverse events), and recommendations whether to continue, modify or stop the study.

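### Serious events that are not life-threatening are classed as ordinary adverse events, and no mesalamine-versus-placebo safety summary is planned

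*Combined protocol and SAP*

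**What the plan says.** The Data Safety and Monitoring section sets the recording rule: "Any untoward medical occurrence in a patient temporarily associated with the use of Lialda whether or not considered related will be recorded". It then defines seriousness and the grouping for safety data in two consecutive sentences: "SAE is defined as life threatening event or death. Safety data will be assessed by the age and race".

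The same section gives the review routes. For the investigator and the ethics board it says: "The study side effects will be reviewed by the PI, and unexpected side effects will be reported to the IRB". The route to the drug company is wider, with no condition on seriousness or expectedness: "All adverse events will be recorded and reported to Shire Developmental Inc". A Data Safety Monitoring Board made up of a physician, a pharmacist and a biostatistician covers adverse and serious adverse events and may recommend continuing, modifying or stopping the study: "The board will meet every 4 months to review the study's progress and endpoints".

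The Design line describes the trial as randomised, double-blind and placebo-controlled. The Statistical Methods section covers the bowel symptom scores, IBS-QOL, binary and ordered efficacy outcomes, exploratory models and missing data. It does not mention adverse events. Its general sentence about comparing the placebo and Lialda groups stands in the paragraph on the intention-to-treat efficacy analysis.

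**The concern.** There are two separate weaknesses.

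First, the definition is closed: it names two kinds of event and nothing elsewhere widens it. Admission to hospital, lasting disability, congenital anomaly and other medically important events are not serious under this rule unless they also threaten life. The trial carries out research endoscopy with biopsy and gives an active drug for 8 weeks, so an admission that is not life-threatening is a plausible event. It would be missing from the serious-event count given to the board and in the final report.

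Second, the grouping named for safety does not use the randomisation. A breakdown by age and race describes who had events. It cannot separate an effect of mesalamine from the background rate in people with IBS. The placebo arm provides that comparison, and the plan does not say it will be used for harm.

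At stake are the accuracy of the serious-event count and what the trial can report about tolerability. The tolerability report matters because the Significance section presents the study as preliminary data for a larger trial.

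**Working it through.** **1. What the definition changes.** Follow two events through the steps that the safety section states.

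| Step | Fatal or life-threatening | Hospitalisation or lasting disability, not life-threatening |
|---|---|---|
| Recorded | yes | yes |
| Reported to the company | yes | yes |
| Reviewed by the investigator | yes | yes |
| Sent to the IRB | if unexpected | if unexpected |
| Seen by the board | yes, 4-monthly | yes, 4-monthly |
| Classed as serious | yes | **no** |

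Only the last row differs. Let A be the number of fatal or life-threatening events and B the number that are serious by the wider criteria but not life-threatening. The plan reports A, and the wider count is A + B. The shortfall is B, which is zero or positive, so the error can only go one way. The documents give no rates from which to estimate B.

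**2. What the grouping leaves out.** The safety section names age and race. The statistical section names the two arms, but only for efficacy outcomes. No section puts arm and adverse events together.

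**3. What a by-arm table could show.** The arm size comes from the Sample Size section, which reproduces:
- Difference: 0.25 × 183 = 45.75. SD: 65.
- n per arm = 2 × (1.96 + 0.84)² × (65 / 45.75)² ≈ 31.7, so 32, as stated.
- With 5% dropout: 64 / 0.95 = 67.4, so 68, or 34 per arm, as stated.

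The event rates below are assumptions, shown as ranges.
- Chance of at least one event among 34 on mesalamine, 1 − (1 − p)³⁴: 29%, 64%, 83% and 97% for true rates of 1%, 3%, 5% and 10%.
- Two-sided Fisher p with k events on mesalamine and none on placebo, 2 × C(34,k) / C(68,k): 0.053 for k = 5 and 0.025 for k = 6. Six events against none are needed for p < 0.05.
- Power of the two-sided Fisher test at 34 per arm, summing the binomial probabilities of all tables with p ≤ 0.05: about 13% for 5% versus 15%, 31% for 5% versus 20%, and 72% for 5% versus 30%.
- With no events in an arm, the exact 95% upper limit is 1 − 0.025^(1/34) = 10.3%.

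A formal test would miss all but a large excess. Counts, percentages and confidence intervals by arm are what this trial can support.

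**The case against.** The strongest reply is that nothing is hidden. Events are recorded regardless of cause, all go to the company, the investigator reviews side effects, unexpected ones go to the IRB, and a board with a biostatistician sees adverse events as well as serious ones. All of that stands. A reader might infer that most serious harms would go unflagged. The documents do not support this: the channels above remain open, and no event rates are given on which to base a word like most.

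A reader might also infer that such events reach the board later than serious ones. The documents state no faster route for serious events, so that does not follow either. As the plan stands, the wider definition changes the classification and the count, and no stated reporting step.

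Third, a reader might take the age-and-race sentence to mean that the arms will be pooled. The text does not say so, and the board could ask for by-arm tables. What remains is that no section promises them, although the plan does state a different grouping.

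Fourth, the recording rule refers to events "temporarily associated with the use of Lialda whether or not considered related will be recorded", which read literally leaves out placebo patients. Under double-blinding staff could not apply it that way, and the section also says that all adverse events are recorded. This is a minor wording point.

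Finally, the low power in the working is a fair argument against formal safety tests. It is no argument against tabulating by arm.

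**Conclusion.** The point holds as a matter of classification and of an unplanned comparison. The stated definition, "SAE is defined as life threatening event or death", makes the serious-event count too low by every event that is serious without threatening life. The stated grouping, "Safety data will be assessed by the age and race", is not enough for a placebo-controlled design, and the statistical section does not make up for it. The documents do not support a claim that harms would go unseen or that by-arm review is ruled out.

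The undercount cannot be sized from the documents. The by-arm comparison would be descriptive at 34 per arm. The conclusion rests on two assumptions: that the safety section is the only place where seriousness is defined, as it is in the text available; and that hospitalisation and lasting disability belong among serious events, a standard that the documents neither cite nor reproduce. The plan should be changed, but the point does not bear on the primary efficacy analysis.

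**What to change.** 1. Extend the serious-event definition to events that are fatal or life-threatening, cause or prolong hospitalisation, cause persistent disability or congenital anomaly, or are otherwise medically important.
2. Replace the age-and-race sentence with a plan for descriptive tables of adverse and serious adverse events by treatment arm (patients with events, percentages and confidence intervals) for the board and the final report. Keep age and race as supportive breakdowns. Add a matching sentence to the statistical section saying that no formal safety test is planned.
3. As a minor wording change, refer in the recording rule to study drug (mesalamine or placebo) instead of Lialda.

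The cost is a few sentences, one extra table and a few more events handled as serious. While the trial is blinded, the by-arm tables should go to the board only. Sample size, treatment and the efficacy analysis are unaffected.

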## **STATISTICAL METHODS, DATA ANALYSIS AND INTERPRETATION:**

### **Sample Size**

The sample size for this trial is based on primary end-point of overall improvement in BSS. A previous IBS treatment trial reported baseline BSS of  $183 \pm 65$ . To detect 25% change in BSS, 32 patients in each group will provide 80% power using two-sided alpha 0.05 comparisons. Assuming 5% drop out rate, we would require a total of 68 patients ( $n=34$  in each group). Assuming proportional estimates for the individual symptoms of IBS, a similar power will be achieved with this sample size.

The Lialda treated group will be compared to the placebo group on improvement in the BBS global symptoms of IBS (continuous scale, range 0 to 400) and BBS individual symptoms of IBS (continuous scales, range 0 to 100). Given the repeated measurements on continuous outcomes, the data will be analyzed with mixed effects linear regression.

Primary analysis will be based on intention to treat. Exploratory analyses assessing "compliers" will also be reported. We will compare the results of placebo and Lialda treated group. The key comparisons between treatment arms will assess changes from baseline to end of treatment using parametric approaches such as the t- test and, when data is highly skewed, nonparametric approaches such as the Wilcoxon test. We note that it is feasible to construct confidence intervals as well as significance tests in the setting of nonparametric comparisons. For some of the secondary efficacy approaches, such as those with binary/ categorical outcomes, follow-up status will be compared between treatment arms using the chi-squared test of the Mantel-Haenszel chi-square for ordered categorical outcomes. Exact versions of these tests will be performed when cell sizes are excessively small.

In addition to the unadjusted primary analyses we will perform exploratory analyses which will use the logistic regression model for binary outcomes, and the linear regression model for continuous outcomes (transformations or categorization may be necessary for the cell count variables). We expect that psychological factors may affect the response to treatment and therefore will do pre-study psychological analysis and will control for them while evaluating response to treatment.

We note that IBS-QOL will be collected at 4-week intervals. Therefore, approaches incorporating repeated measures, notably the linear mixed model, will be implemented to assess and quantify trends (e.g., a linear divergence between treatment arms) over time. These approaches also allow the inclusion of available data from patients who drop out in the middle of the study in the analysis. We are aware, however, that the dropout pattern in this study may not be the "Missing at Random" pattern required for such available-data models to yield valid inference. We will examine and report characteristics of study completers versus dropouts, to obtain some empirical evidence for or against this missingness assumption.

We are familiar with imputation approaches, and will implement these when appropriate. Simplistic approaches such as substituting each subject's "worst" value, or the "worst" value observed for any subject, for missing values may shed light on the robustness of any significant findings to missing data. However, such substitution approaches are not useful for formal statistical inference.

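### The key BSS comparison does not adjust for baseline BSS, and the mixed model's relation to it is unstated; naming one baseline-adjusted week 8 contrast is a nearly free improvement

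*Combined protocol and SAP*

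**What the plan says.** Study End-points makes improvement in overall BSS after 8 weeks of treatment the primary endpoint. The analysis is described in the Sample Size section, in this order:

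- For BSS global and individual symptoms: "Given the repeated measurements on continuous outcomes, the data will be analyzed with mixed effects linear regression". No model terms, covariance structure or week 8 contrast are given.
- On the analysis set: "Primary analysis will be based on intention to treat".
- The "key comparisons between treatment arms will assess changes from baseline to end of treatment using parametric approaches such as the t- test", with a Wilcoxon test as the alternative when skewness is high. No cut-off for skewness is stated.
- On tiers: "In addition to the unadjusted primary analyses we will perform exploratory analyses". These exploratory analyses are logistic and linear regression models.
- On covariates, the plan expects psychological factors to matter and "will do pre-study psychological analysis and will control for them while evaluating response to treatment". No other covariate is named.

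The power statement is: "To detect 25% change in BSS, 32 patients in each group will provide 80% power using two-sided alpha 0.05 comparisons". Treatment Schedule and the study procedures table show BSS collected at the start, at week 4 and at the end of treatment.

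**The concern.** Two things are left open or left unused.

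First, the plan has a partial order (key comparisons, unadjusted primary analyses, exploratory regressions), but it does not place the BSS mixed model in that order. A reader cannot tell whether the mixed model replaces the t-test, supports it or is secondary to it.

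Second, baseline BSS enters the key comparison only by subtraction, which fixes its coefficient at 1. Estimating that coefficient is at least as precise, apart from about one degree of freedom, and is much more precise when baseline and week 8 scores are weakly correlated. A weak correlation is possible here. Baseline BSS is taken at the first visit, screening can last up to 8 weeks and treatment lasts 8 weeks, so the two scores can be about 16 weeks apart.

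At stake is power in a trial of 68 patients, lost with no saving in return.

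**Working it through.** **Inputs from the Sample Size section.** Baseline BSS 183, SD 65; difference 25% × 183 = 45.75; two-sided alpha 0.05; 32 per arm analysed, 34 per arm randomised. **Assumed:** the correlation ρ between baseline and week 8 BSS and, for the main results, SD 65 at both visits.

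**The plan's own figure.** n per arm = 2 × [65 × (1.960 + 0.842) / 45.75]² = 31.7, rounded up to 32. Power at 32 per arm is 80.4% by the normal approximation and 79.1% by the noncentral t. The figure reproduces. The 65 used is the SD of a single-visit score.

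**Formulas for the two analyses.**
- Change score: SD = 65 × √(2(1 − ρ)), 62 degrees of freedom.
- Baseline-adjusted week 8 score: SD = 65 × √(1 − ρ²), 61 degrees of freedom.
- Noncentrality = 45.75 / (SD × √(2/32)) = 183 / SD. For example, at ρ = 0.3 it is 183/76.9 = 2.38 versus 183/62.0 = 2.95.

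| ρ (assumed) | SD, change | SD, adjusted | Power, 32 per arm | Power, 61 patients | n per arm for 80% |
|---|---|---|---|---|---|
| 0.3 | 76.9 | 62.0 | 64.9% vs 82.8% | 62.7% vs 80.9% | 46 vs 30 |
| 0.5 | 65.0 | 56.3 | 79.1% vs 89.2% | 77.1% vs 87.7% | 33 vs 25 |
| 0.7 | 50.3 | 46.4 | 94.7% vs 97.3% | 93.7% vs 96.6% | 21 vs 18 |
| 0.8 | 41.1 | 39.0 | 99.2% vs 99.6% | – | – |

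In each pair the unadjusted change score comes first. The 61-patient column applies the 10% dropout given under Time Line (68 × 0.9 = 61.2).

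With equal SDs, the change score matches the plan's 80% only when ρ is about 0.5 or more. The adjusted analysis has at least the plan's own 79.1% at any ρ from 0 up.

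**Unequal SDs.** With baseline SD 65 and week 8 SD s, the variance of change minus the adjusted variance is (65 − ρs)², which is never negative. It nearly vanishes when ρs is close to 65.
- s = 50: the gain is 22.4 points at ρ = 0.3 (74.1% vs 96.5%).
- s = 80: power is 87.6% vs 88.3% at ρ = 0.7, a gain of about 0.7 points. At ρ = 0.8 the gain is nil, since 0.8 × 80 = 64.

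**If 65 is read as the SD of change.** The adjusted SD is 65 × √((1 + ρ)/2) = 52.4, 56.3 and 59.9. Power is 79.1% unadjusted versus 93.0%, 89.2% and 85.2% at ρ = 0.3, 0.5 and 0.7.

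**Does the mixed model supply the adjustment by itself?** No. With complete data at weeks 0, 4 and 8, all three scores as outcomes and free arm means at each visit, the fitted means are the observed means. The week 8 contrast against baseline is then exactly the difference in mean change. Baseline must be a covariate, or its mean must be held equal across arms.

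**Constrained longitudinal model, approximate.** In simulation with 68 randomised and 61 week 8 values, power was about 81%, 88% and 97% at ρ = 0.3, 0.5 and 0.7. That fit used an EM algorithm and a t reference with 58 degrees of freedom, not restricted maximum likelihood with Kenward-Roger, so these values are a guide only. Without a small-sample correction, simulated type I error was 5.2–5.7%.

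**The case against.** The strongest reply is that the plan does order its analyses. The endpoint and week 8 are fixed, the t-test on change is called key, the primary analyses are called unadjusted, and regressions are exploratory. The natural reading is a t-test on week 8 change. A reader might infer from the mixed-model sentence that the primary result is not fixed in advance. The documents do not support that: what is open is the role of one sentence and an undefined skewness trigger.

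The practical effect of that gap is also usually small. In simulation with equal correlations across visits, the change t-test and an unadjusted random-intercept model disagreed at p = 0.05 in 4.0%, 2.9% and 1.2% of trials at ρ = 0.3, 0.5 and 0.7, and in none with an unstructured covariance. Disagreement reached 10.2%, 8.2% and 3.0% only under two added assumptions: a random intercept alone, and correlation that decays between visits. The plan states neither.

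A reader might also infer that the key test is wrong or that the trial is underpowered. Neither follows. The change-score test is valid, and its simulated type I error was 4.9–5.1%. Whether it falls short of 80% power depends on a correlation the documents do not give; the 16-week gap shows only that a low value is possible.

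All of this stands. It limits the point to efficiency and clarity. It does not remove the power given up at low to moderate correlation, and it does not tell the analyst what the mixed model is for.

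**Conclusion.** This is a free improvement, not an error of validity. The plan partly tiers its BSS analyses, leaves the mixed model's role unstated, and does not use baseline BSS as a covariate. On the plan's inputs with equal SDs, adjustment adds about 18, 10 and 2.5 points of power at correlations of 0.3, 0.5 and 0.7, and under 1 point at 0.8. Across the settings checked, adjustment was never behind to one decimal, but the gain can fall to nil (week 8 SD 80, correlation 0.8). The size rests on the assumed correlation and on how the 65 is read; the missing link between mixed model and t-test rests on neither. If a baseline-adjusted mixed model was intended all along, only the naming gap remains.

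**What to change.** In the Sample Size section, replace the reference to unadjusted primary analyses, as far as BSS is concerned, with one named analysis. Suggested wording:

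*The primary analysis is the difference between arms in total BSS (0–400) at week 8, adjusted for baseline BSS, in all randomised patients by assigned arm, with a 95% confidence interval.*

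Then name one of two methods:
- a mixed model of BSS at weeks 4 and 8, with baseline either a covariate or constrained equal across arms, categorical visit, arm by visit, unstructured covariance and a small-sample degrees-of-freedom correction such as Kenward-Roger; or
- ANCOVA of week 8 BSS on baseline BSS, with a stated method for missing week 8 values. The present text says only "We are familiar with imputation approaches, and will implement these when appropriate".

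Report the t-test and the Wilcoxon test on change as sensitivity analyses, both of them and whatever the skewness, and say that any model controlling for psychological factors is exploratory.

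The cost is wording and about one degree of freedom (62 to 61 with 64 patients). BSS at baseline, week 4 and week 8 is already collected, and the sample size need not change.

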## **ADMINISTRATIVE RESPONSIBILITIES:**

### **Study Resources:**

Study procedures will be conducted at the University of Utah Hospital and the VA Medical Center. The data gathered for the study at the University of Utah will be stored in the Division of Gastroenterology at The University of Utah Hospital. Data collected at the VA Medical Center will be stored in the Gastroenterology Division of the VA Medical Center. The data analysis for all patients will be conducted at the University of Utah. All information will be de-identified and securely transferred to the University of Utah for analysis. Confidentiality and privacy of patient's research data (patient's demographics) will be maintained by saving the documents in locked cabinets and keeping them in secure files in the GI research offices. The computerized data will be saved on password-protected computers, also in secured research offices. The principal investigator, co-investigator, study coordinator, and research staff, will have access to this data. The patients' names will not be recorded in this database. Patients will be identified by an assigned number and patient's initials only. The database will be password-protected to ensure security.

The data and results of the study may be published or presented. In this case, patients' will be identified by number only in order to maintain confidentiality. The data will be stored indefinitely.

For data verification purposes, authorized representatives, a regulatory authority, or IRB may require direct access to parts of the hospital or practice records relevant to the study, including patients' medical history. The principal investigator, co-investigators study coordinator and research staff as well as the Federal Drug Administration, a regulatory agency, will also have access to patient's information and collected data.

Subjects will be given the opportunity to read the consent form and ask questions to the study staff until subjects express that they fully understand the consent form and their responsibilities for participation in the study. Subjects will sign and date the consent form and will be given a copy of the consent form to keep. No study procedures will be performed until the consent form is signed. The data and results of the study may be published or presented. In this case, patients will be identified by number only in order to maintain confidentiality.

